11.3 Exploratory Endpoints

The following additional endpoints will be evaluated and compared in the Intervention group vs. Control group at the end of the 13-week randomized period:

- Proportion of participants with A1C <7%
- Proportion of participants with A1C <8%
- Proportion of participants with $\geq 1\%$ improvement in A1C from baseline
- Proportion of participants with ≥ 10 relative percentage point improvement in A1C from baseline
- Proportion of participants with either $\geq 1\%$ improvement in A1C from baseline OR ≥ 10 relative percentage point improvement in A1C from baseline
- Change from baseline in Body Mass Index (BMI)
- Change from baseline in total daily insulin (TDI) (units/kg)
- Additional CGM-derived endpoints, such as coefficient of variation, time above range >250 mg/dL, percentage of time < 54 mg/dL (superiority), TIR during daytime and nighttime hours
- Number of episodes of severe hypoglycemia
- Number of episodes of DKA

11.4 Patient-Reported Outcomes

The following questionnaires will be used to evaluate general and disease-specific quality of life, and device usability. Results will be assessed at 13 weeks compared to baseline (Intervention and Control group).

- Clarke hypoglycemia awareness questionnaire - Used to assess impaired awareness of hypoglycemia
- EQ-5D-3L – Used to measure quality of life
- T1-DDS¹ – Used to measure four critical dimensions of distress
- DQOL-brief² – Used to assess the relative burden of an intensive diabetes treatment regimen

- DIDP – Used to assess the perceived impact of diabetes in physical health, finances, relationships with family/friends, leisure activities, work/studies and emotional well-being
- HCS³ –Used to measure hypoglycemia unawareness, hypoglycemia frequency, severity, and impact
- PSQI – Used to measure sleep disturbance and usual sleep habits
- SUS – Used to measure usability of a system
- INSPIRE – Used to evaluate the impact of AID systems on the psychosocial functioning and quality of life

Any endpoint that is not listed as a Primary, Secondary, or Exploratory endpoint will be treated as exploratory.

11.5 Sample Size

The study is powered at 90% to detect a between-group difference of 10% in TIR 70-180 mg/dL and assuming a standard deviation of 16.5% in each group. Under these assumptions and with 2:1 Intervention:Control randomization, a total sample size of 131 participants is required (87 Intervention, 44 Control). To allow for pre-randomization attrition of up to 15%, and post-randomization attrition of up to 22.9%, a total sample size of up to 200 will be enrolled to obtain 170 randomized participants with 131 participants completing the 13 weeks. The anticipated difference in TIR 70-180 mg/dL was projected from the OP5 pivotal study. PASS 2022 was used for sample size calculations.

11.6 Analysis Sets

The following analysis sets are planned for the study:

11.6.1 ITT (Intention to Treat) Analysis Set

The ITT analysis set includes all participants that are enrolled in the study. All safety analyses will be based on the ITT analysis set.

11.6.2 mITT (modified Intention to Treat) Analysis Set

The modified Intention to Treat (mITT) analysis set is a subset of the ITT analysis set. The mITT analysis set will consist of all participants who have been randomized. The mITT analysis set will be used as the primary analysis for the primary and secondary endpoints and for other clinical outcome data.

11.7 PP (Per-Protocol) Analysis Set

The Per-Protocol (PP) analysis set is a subset of the mITT analysis set. Participants will be included in the PP analysis set if they have a minimum of 80% system use as measured by the study CGM (control group) or Omnipod 5 (intervention group) during the 13-week randomized period over a minimum duration of 10 weeks and have completed the study without major protocol deviations. The PP analysis set will be used as supportive analysis for the endpoints. The following will be considered major protocol deviations:

- Major inclusion/exclusion criterion deviation

- Significant protocol non-compliance that may confound the study objective data (e.g., use of prohibited medications, not using control group pump for prolonged period)

The list of participants excluded from the PP analysis set will be determined prior to analysis while blinded to treatment group. If the PP analysis set does not differ from the mITT analysis set, separate analyses will not be presented.

11.8 Analysis of Primary and Secondary Endpoints

The primary endpoint will be tested for statistical significance in the mITT analysis set at a two-sided significance level of .5%. Hypothesis testing for the secondary endpoints will commence if and only if the primary endpoint is found to be statistically significant (i.e. two-sided p-value ≤ 0.05). Strict control of Type I error will be maintained with a hierarchical testing procedure, with secondary endpoints tested in the following order:

- Percentage of time <54 mg/dL (non-inferiority)
 - If the upper bound of the two-sided 95% confidence interval for the difference (μ_i minus μ_c) is $<1\%$, non-inferiority will be established. If the upper bound of the two-sided 95% confidence interval for the difference (μ_i minus μ_c) is $<0\%$, superiority of the Intervention group compared to the Control group will be established.
- Percentage of time >180 mg/dL
- Mean glucose
- Change from baseline in A1C
- Percentage of time < 70 mg/dL
- Change from baseline in Type 1-Diabetes Distress Scale (T1-DDS) total score at 13 weeks
 - If change from baseline in T1-DDS total score at 13 weeks is found to be statistically significantly different in the Intervention group compared to the Control group, the proportion of subjects in each treatment group achieving an improvement of ≥ 0.19 points (MCID) in the T1-DDS total score at 13 weeks will also be compared.
- Change from baseline in Hypoglycemia Confidence Scale (HCS) total score at 13 weeks
 - If change from baseline in HCS total score at 13 weeks is found to be statistically significantly different in the Intervention group compared to the Control group, the proportion of subjects in each treatment group achieving a score of ≥ 3 points in the HCS total score at 13 weeks will also be compared.
- Change from baseline in Diabetes Quality of Life-brief (DQOL-brief) total score at 13 week
 - If change from baseline in DQOL-brief total score at 13 weeks is found to be statistically significantly different in the Intervention group compared to the Control group, the proportion of subjects in each treatment group achieving a clinically meaningful improvement (defined as ≥ 0.5 *standard deviation of change from baseline in DQOL-brief total score at 13 weeks) in the DQOL-brief total score at 13 weeks will also be compared.

Each endpoint with a two-sided p-value of ≤ 0.05 (equivalent to one-sided p-value ≤ 0.025) is considered to be met until a secondary endpoint with a two-sided p-value of

>0.05 (equivalent to one-sided p-value > 0.025) is encountered. That secondary endpoint, and all subsequent secondary endpoints, are considered to not be met irrespective of their observed p-values.

There will be no formal hypothesis testing for the exploratory endpoints.

The primary, secondary, and additional endpoints will be summarized for the mITT and PP analysis sets. If the PP analysis set does not differ from the mITT analysis set, separate analyses will not be presented.

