12.5 General Statistical Methods

Standard statistical methods will be employed to analyze all data. Data collected in this study will be presented using summary tables and participant data listings. Unless otherwise noted, all p-values will be considered significant at a two-sided significance level of 5%. Continuous variables will be summarized using descriptive statistics, including count, mean, median, standard deviation (SD), minimum and maximum. Where appropriate, 95% two-sided confidence intervals for the means or medians will be presented. If the observed data are found not to follow a normal distribution, appropriate non-parametric methods may be employed. Categorical variables will be summarized by frequencies and percentages. Unless explicitly stated otherwise, percentages will utilize a denominator corresponding to the number of unique participants.

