4 ANALYSIS OF PRIMARY ENDPOINT

4.1 SAMPLE SIZE

The sample size estimation is based on the following assumptions:

- Power of 90% and two-sided significance level of 5%
- Difference between groups of 10% in TIR 70-180 mg/dL
- Standard deviation of 16.5% in each group
- 2:1 randomization (Intervention:Control)

Under these assumptions, a total sample size of 131 participants is required (87 Intervention, 44 Control). To allow for pre-randomization attrition of up to 15%, and post-randomization attrition of up to 22.9%, a total sample size of up to 200 will be enrolled to give 170 participants randomized and 131 participants completing the 13 weeks. The anticipated difference in TIR 70-180 mg/dL was projected from the OP5 pivotal study.

The sample size calculations were performed using PASS 2021.

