Standard residual diagnostics will be performed for all analyses. It is expected that the primary outcome will follow an approximately normal distribution, however, residual values will be examined to confirm an approximate normal distribution. If values are highly skewed, then robust regression using M-estimation will be used instead. In this case, the model will include TIR 70-180 mg/dL during the 13 weeks randomized period as the dependent variable, baseline TIR 70-180 mg/dL as a covariate, and missing data will be handled using multiple imputation.

The primary analysis will utilize the mITT analysis set and will be tested at a two-sided significance level of 5%.

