5 ANALYSIS OF OTHER ENDPOINTS

5.1 ANALYSIS OF SECONDARY ENDPOINTS (PERIOD 1)

To preserve the family-wise type 1 error for selected key secondary endpoints, a fixed sequence hierarchical testing approach will be used. If the primary endpoint is found to be statistically significant at a two-sided significance level of 5%, testing for secondary endpoints can commence. Secondary endpoints will be tested in a hierarchical fashion at a one-sided significance level of 2.5% (or two-sided significance level of 5% as appropriate). Each endpoint with a two-sided p-value ≤ 0.05 (or one-sided p-value of ≤ 0.025 , as appropriate) is considered to be met until a secondary endpoint with a two-sided p-value ≥ 0.05 (or one-sided p-value of ≥ 0.025 , as appropriate) is encountered. This process continues iteratively moving to the next endpoint down on the list until a non-significant result is observed, or all endpoints have been tested. If a non-significant result is encountered, then formal statistical hypothesis testing is terminated and any variables below on the list are not formally tested.

Regardless of the results of the hierarchical testing, summary statistics appropriate to the distribution will be tabulated for each key secondary endpoint by treatment group. A 95% confidence interval for the treatment effect will also be calculated for all key secondary outcomes listed above. However, a confidence interval that is below zero (superiority) or that is below the non-inferiority margin (noninferiority) will not be considered a statistically significant result if an outcome variable higher on the hierarchical list failed to reach statistical significance.

The secondary endpoints will be analyzed using a repeated measures linear mixed effects model with the endpoint at baseline and at 13 weeks as the dependent variable. The correlation between baseline and follow-up will be modelled using an unstructured covariance matrix. The model will include randomized treatment group, age, sex, and duration of diagnosis as fixed effects and site as a random effect. This model adjusts for baseline value of the endpoint by forcing the treatment groups to have the same mean value at baseline. Missing data will be handled by using a direct likelihood approach which will allow participants to be included even if they only have data at one of the time points.

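### Protocol 11.8 prints the primary test level as two-sided .5%, while its own next sentence, protocol 12.5, the SAP and the sample size all use 5%

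*Protocol*

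**What the plan says.** Protocol 11.8 sets the primary test, in the mITT set, "at a two-sided significance level of .5" per cent. The next sentence starts secondary testing "if and only if the primary endpoint is found to be statistically significant (i.e. two-sided p-value ≤ 0.05"). The end of the section applies the same 0.05 cut-off to each endpoint in the hierarchy.

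The other statements of the level agree with 0.05:

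- Protocol 12.5, as a default unless otherwise noted: "all p-values will be considered significant at a two-sided significance level of 5" per cent.
- SAP 4.1, for the sample size: "Power of 90% and two-sided significance level of 5" per cent.
- SAP 4.2, for the primary test: "The primary analysis will utilize the mITT analysis set and will be tested at a two-sided significance level of 5" per cent.
- SAP 5.1, for the gate: "If the primary endpoint is found to be statistically significant at a two-sided significance level of 5%, testing for secondary endpoints can commence".

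Protocol 11.5 gives power, difference, standard deviation, allocation and total, but no significance level: "The study is powered at 90% to detect a between-group difference of 10% in TIR 70-180 mg/dL", with SD 16.5 and 2:1 allocation, requiring 131 participants (87 and 44).

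Protocol 12.7 and SAP 1 both say that the SAP prevails where the two documents disagree.

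**The concern.** Two adjacent sentences of protocol 11.8 give thresholds for the same test that differ tenfold (0.05 / 0.005 = 10). Read literally, a primary p-value between 0.005 and 0.05 fails the test in the first sentence and opens the secondary hierarchy in the second.

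The number matters. SAP 2.4 ties study success to the primary endpoint alone, and the same result is the gate to every secondary claim. Someone holding only the protocol, such as an ethics committee or a journal reviewer, meets two criteria and finds no level in 11.5 to choose between them. Section 12.5 does not settle it either: its 5% is a default that yields to a specific statement elsewhere, and 11.8 is such a statement.

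**Working it through.** **Inputs.** Difference 10 percentage points of TIR, SD 16.5 in each group, power 90%, 2:1 allocation, 87 + 44 = 131 completers (protocol 11.5, SAP 4.1). Candidate two-sided levels: 0.05 (SAP 4.1, 4.2, 5.1; protocol 12.5 and the second sentence of 11.8) and 0.005 (first sentence of 11.8).

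**1. Reproduce the plan's figure at 5%.**

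Normal approximation, control-group size with ratio 2:1:

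n_C = (1 + 1/2) × [SD × (z₁₋α/₂ + z₀.₉₀) / difference]²

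= 1.5 × [16.5 × (1.960 + 1.282) / 10]² = 42.9, so 43, for a total of 3 × 43 = 129.

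The t-test version adds a little. The noncentrality parameter at 87/44 is

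10 / [16.5 × √(1/87 + 1/44)] = 10 / (16.5 × 0.1850) = 3.276, on 129 degrees of freedom.

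With critical value 1.979 this gives power 90.2%. Taking the split nearest to 2:1 at each total, 131 (87 + 44) is the smallest total that reaches 90%. The plan's figure reproduces exactly.

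**2. The same calculation at 0.5%.**

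Normal approximation: n_C = 1.5 × [16.5 × (2.807 + 1.282) / 10]² = 68.3, so 69, for a total of 207.

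Noncentral t: the critical value rises to 2.856. The smallest total at the split nearest to 2:1 is 209 (139 + 70).

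| Two-sided level | Power at 87/44 | Power at 113/57 (all 170 randomized) | Total for 90% power |
|---|---|---|---|
| 5% | 90.2% | 96.0% | 131 |
| 0.5% | 66.2% | 81.0% | 209 |

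(Powers and totals by noncentral t. The normal approximation at 87/44 gives 90.6% and 68.1%.)

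**3. Could another level give 131?** By the normal formula, one-sided 5% gives 105, which does not match. One-sided 2.5% gives 129, but for sizing that is the same as two-sided 5%. Of the levels tried, only two-sided 5% (or its one-sided 2.5% equivalent) fits.

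**4. Attrition.** 200 × 0.85 = 170, and 170 × (1 − 0.229) = 131.07. The enrolment chain is built on 131. At 0.5% the requirement of about 209 evaluable would exceed the 170 to be randomized and the 200 to be enrolled.

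**The case against.** The best case against the point is that it is already resolved. Protocol 12.7 and SAP 1 give the SAP precedence, and the SAP states "will be tested at a two-sided significance level of 5" per cent for the primary analysis and uses the same level for sizing and gating. The .5% is very probably a stray character: nothing elsewhere supports an intended 0.5% test, and protocol 11.2 carries similar editing residue, where the T1-DDS improvement reads as both 0.19 and 2 points. A spurious mark from reading the PDF cannot be excluded either; a look at the source file would settle that. Taken literally, the slip is also conservative and could not inflate the type I error of the primary test.

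Most of this stands, and it limits the point to a correction of the text. It does not remove it. A precedence rule says which document wins, but the protocol would still print two thresholds for its primary test.

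Two stronger readings are tempting:

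- *The trial is underpowered.* A reader might infer this from the 66.2%. The documents do not support it: that power applies only if the test were run at 0.5%, which the SAP rules out.
- *The outcome for a p-value between 0.005 and 0.05 is undecided.* Under the SAP such a result meets the primary endpoint, and the gate in protocol 11.8 is itself written at 0.05. The conflict lies in one sentence of the protocol.

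**Conclusion.** The .5% in protocol 11.8 is wrong as written. It contradicts the sentence after it, protocol 12.5 and three sections of the SAP, and it cannot coexist with 90% power at 131 completers.

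The effect on the trial is nil: the operative level is two-sided 5%, and sample size, power and planned analysis stay as they are. The 0.5% results serve only to show which of the two printed figures is in error. They rest on the plan's own difference and SD and on a two-sample t-test without covariate adjustment, which reproduces the plan's total. That only 5% is operative rests on the precedence rule stated in both documents.

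This is an internal inconsistency in a figure that decides the primary result. It is worth correcting because of where it sits, although its practical reach is small.

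**What to change.** In protocol 11.8, change .5% to 5%. In protocol 11.5, add that the sample size assumes a two-sided significance level of 5%, as SAP 4.1 already does. The protocol then carries one threshold for the primary endpoint, the same as the SAP's.

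The cost is one character and one short phrase. No change to the SAP, the sample size or study conduct follows. Because protocol 14.6 requires ethics approval before an amendment is implemented, a stand-alone amendment would be out of proportion; the next revision or a clarification letter is enough, preferably before the primary results are known. If the trial has already been analysed, a sentence in the study report that two-sided 5% was the prespecified level, citing the SAP, would do.

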12 PERCENTAGE OF TIME ENDPOINTS

The primary endpoint and the secondary endpoints that summarize time in specific glycemic ranges will be calculated from device data outputs as follows:

$$100 \times \frac{\# \text{ of CGM records in range}}{\# \text{ of evaluable CGM records}} = \% \text{ of time}$$

12.1 Subgroup Analyses

Summary statistics will be stratified by time points of interest (e.g., day vs. night, overall). Any additional subgroup analyses will be detailed in the SAP.

12.2 Additional Data Analyses

CGM and Omnipod 5 device data will be made available to Sponsor representatives for periodic reviews. Reviews of the controller data will be conducted to identify any anomalies and to confirm the algorithm appears to be functioning as expected. These reviews, including any findings, will be documented. Unless potential safety concerns are identified, the results of such reviews will not be shared with study sites or participants and thus, will not impact study endpoints. Should a potential safety concern be identified, sites may be notified as appropriate to ensure participant safety and measures may be taken to address the issue such as, but not limited to, changes to the protocol and/or device. Any resulting device deficiencies will be reported, if applicable. A brief summary of the controller data reviews will be included in the final clinical study report.

12.3 Safety Analyses

12.3.1 Evaluation of Adverse Events

All adverse events reported over the course of the study will be summarized and tabulated by study phase (standard therapy or 13-week follow-up), event category, seriousness, severity, and relationship to the study procedure and the devices. For the purposes of summarization, an event will be considered "Related" if the relationship was deemed as "Possibly Related" or "Related". In cases where the same event is reported more than once per participant, the event will only be counted once in the incidence table(s).

Adverse events leading to death or to discontinuation from the study will be listed separately. A listing of all adverse events will be provided.

12.3.2 Evaluation of Device Deficiencies

Device deficiencies will be tabulated and listed in a manner similar to the methods described for adverse events. Any device deficiency leading to an AE or to study termination will be listed separately.

12.3.3 Episodes of Severe Hypoglycemia and DKA

The number of severe hypoglycemia and DKA adverse events, and the number and percent of subjects with at least one event in each group will be summarized. Statistical testing will be performed for the rate of SH (and DKA) if there are ≥ 5 events (of SH or DKA, respectively) combined across both treatment groups. The rates will be calculated as the number of events per 100 person years.

12.4 Baseline Characteristics

The distribution of each baseline characteristic or demographic parameter of interest (such as age, gender, medical history, etc.) will be presented. Data on all enrolled participants will be presented. Continuous variables will be summarized using count, mean, median, standard deviation, and range. Categorical variables will be summarized using counts and percentages.

12.5 General Statistical Methods

Standard statistical methods will be employed to analyze all data. Data collected in this study will be presented using summary tables and participant data listings. Unless otherwise noted, all p-values will be considered significant at a two-sided significance level of 5%. Continuous variables will be summarized using descriptive statistics, including count, mean, median, standard deviation (SD), minimum and maximum. Where appropriate, 95% two-sided confidence intervals for the means or medians will be presented. If the observed data are found not to follow a normal distribution, appropriate non-parametric methods may be employed. Categorical variables will be summarized by frequencies and percentages. Unless explicitly stated otherwise, percentages will utilize a denominator corresponding to the number of unique participants.

12.6 Missing Data

All practical monitoring and follow-up steps will be taken to ensure complete and accurate data collection.

Due to the nature of the data and study design, it is anticipated that all randomized subjects will contribute some CGM data post-randomization. Hence, it is possible that there will be no need for imputation of missing values for the CGM endpoints. A subject will be included in analysis of CGM endpoints in the mITT analysis set only if the subject provides at least seven days' worth of sensor readings during the course of 13 weeks. This is equivalent to 2016 readings, assuming CGM readings are taken at approximately every five minutes for a total of 288 readings per day. No additional imputations for missing data are planned for the primary endpoint, and secondary endpoints involving CGM data. Missing records (i.e. gaps in data) will not be imputed for either the intervention or control group.

CGM values for other reasons will not be imputed.

It is likely that at least some subjects do not contribute data for the A1C and patient-reported outcome endpoints (e.g., due to early withdrawal).

For the main analysis of A1C and patient-reported outcomes, missing values for the subjects in the mITT analysis set will be imputed using the subject's last known A1C/ePRO value if collected within the analysis window (such as during Early Withdrawal visit). The analysis windows are assigned as follows:

- A1C à 13±2 weeks from start of the 13-week randomized period
- PROs à 13±5 weeks from start of the 13-week randomized period

Questionnaire scoring will follow the scoring guidelines; PRO scores either at baseline or at 13 weeks that are missing for other reasons (e.g., due to unanswered questions) will not be imputed. No imputation for missing data will be included in the analyses based on Per Protocol analysis set. Additional sensitivity analyses will be detailed in the SAP.

